3.3. Strata and Covariates

This study does not use a stratified randomization schedule when enrolling subjects. No covariates will be included in efficacy and safety analyses.

3.4. Examination of Subject Subgroups

There are no prespecified subject subgroupings for efficacy and safety analyses.

3.5. Multiple Comparison

Adjustments for multiplicity will not be made, because no formal statistical testing will be performed in this study.

3.6. Missing Data and Outliers

3.6.1. Missing Data

In general, missing data will not be imputed unless methods for handling missing data are specified.

For missing last dosing date of study drug, imputation rules are described in Section 4.2. The handling of missing or incomplete dates for AE onset is described in Section 7.1.5.2, and for prior and concomitant medications in Section 7.4.

3.6.2. Outliers

Outliers will be identified during the data management and data analysis process, but no sensitivity analyses will be conducted. All data will be included in the data analysis.

3.7. Data Handling Conventions and Transformations

The following conventions will be used for the imputation of date of birth when it is partially missing or not collected:

- If only month and year of birth is collected, then “15” will be imputed as the day of birth
- If only year of birth is collected, then “01 July” will be imputed as the day and month of birth
- If year of birth is missing, then date of birth will not be imputed

In general, age (in years) collected at screening visit will be used for analyses and presented in listings. If age at screening is not available for a subject, then age derived based on date of birth and the screening visit date will be used instead. If an enrolled subject was not dosed with any study drug, the randomization date will be used instead of the screening visit date. For screen failures, the date the first informed consent was signed will be used for the age derivation. Age required for longitudinal and temporal calculations and analyses (eg, estimates of creatinine clearance, age at date of AE) will be based on age derived from date of birth and the date of the measurement or event, unless otherwise specified.

Non-PK data that are continuous in nature but are less than the lower limit of quantitation (LOQ) or above the upper LOQ will be imputed as follows:

- A value that is 1 unit less than the lower LOQ will be used to calculate descriptive statistics if the datum is reported in the form of “< x” (where x is considered the LOQ). For example, if the values are reported as < 50 and < 5.0, values of 49 and 4.9, respectively, will be used to calculate summary statistics. An exception to this rule is any value reported as < 1 or < 0.1, etc. For values reported as < 1 or < 0.1, a value of 0.9 or 0.09, respectively, will be used to calculate summary statistics.
- A value that is 1 unit above the upper LOQ will be used to calculate descriptive statistics if the datum is reported in the form of “> x” (where x is considered the LOQ). Values with decimal points will follow the same logic as above.
- The lower or upper LOQ will be used to calculate descriptive statistics if the datum is reported in the form of “≤ x” or “≥ x” (where x is considered the LOQ).

Natural logarithm transformation will be used for analyzing concentrations in intensive PK samples. Concentration values that are BLQ will be presented as “BLQ” in the concentration data listing. Values that are BLQ will be treated as 0 for summary purposes.

The following conventions will be used for the presentation of summary and order statistics for intensive PK concentrations:

- If at least 1 subject has a concentration value of BLQ for the time point, the minimum value will be displayed as “BLQ.”
- If more than 25% of the subjects have a concentration data value of BLQ for a given time point, the minimum and Q1 values will be displayed as “BLQ.”
- If more than 50% of the subjects have a concentration data value of BLQ for a given time point, the minimum, Q1, and median values will be displayed as “BLQ.”
- If more than 75% of the subjects have a concentration data value of BLQ for a given time point, the minimum, Q1, median, and Q3 values will be displayed as “BLQ.”
- If all subjects have concentration data values of BLQ for a given time point, all order statistics (minimum, Q1, median, Q3, and maximum) will be displayed as “BLQ.”

PK concentrations that are BLQ will be excluded before log transformation or statistical model fitting.

3.8. Analysis Visit Windows

3.8.1. Definition of Study Day

Study day will be calculated from the first dosing date of study drug and derived as follows:

- For postdose study days: Assessment Date – First Dosing Date + 1
- For days prior to the first dose: Assessment Date – First Dosing Date

Therefore, study day 1 is the day of first dose of study drug administration.

3.8.2. Analysis Visit Windows

The nominal visit as recorded on the CRF will be used when data are summarized by visit. Any data relating to unscheduled visits will not be assigned to a particular visit or time point.

However, the following exceptions will be made:

- An unscheduled visit prior to the first dosing of study drug may be included in the calculation of the baseline value, if applicable.
- Unscheduled visits after the first dosing of study drug will be included in determining the maximum postbaseline toxicity grade.

- For subjects who discontinue from the study treatment, the EOT visit data will be assigned to what would have been the next scheduled visit where the respective data were scheduled to be collected.

3.8.3. Selection of Data in the Event of Multiple Records in an Analysis Visit Window

Depending on the statistical analysis method, single values may be required for each analysis window. For example, change from baseline by visit usually requires a single value, whereas a time-to-event analysis would not require 1 value per analysis window.

If multiple valid, nonmissing measurements exist in an analysis window, records will be chosen based on the following rules if a single value is needed:

- For baseline, the last nonmissing value on or prior to the first dosing date of study drug will be selected, unless specified differently. If there are multiple records with the same time or no time recorded on the same day, the baseline value will be the average of the measurements for continuous data, or the measurement with the lowest severity (eg, normal will be selected over abnormal for safety electrocardiogram [ECG] findings) for categorical data.
- For postbaseline values:
 - The record closest to the nominal day for that visit will be selected.
 - If there are 2 records that are equidistant from the nominal day, the later record will be selected.
 - If there is more than 1 record on the selected day, the average will be taken for continuous data and the worse severity will be taken for categorical data, unless otherwise specified.

4. SUBJECT DISPOSITION

4.1. Subject Enrollment and Disposition

A summary of subject enrollment will be provided by treatment arms for each country and overall based on all enrolled subjects. The summary will present the number and percentage of subjects enrolled. For each column, the denominator for the percentage calculation will be the total number of subjects analyzed for that column.

A summary of subject disposition will be provided by treatment arms based on All Screened Subjects. This summary will present the number and percentage of subjects in the following categories:

- Screened Subjects
- All Enrolled Subjects
- ITT Analysis Set
- Safety Analysis Set
- PK Analysis Set
- Study Drug Completion Status
 - Discontinued Study Drug
- Reasons for Discontinuation of Study Drug
- Study Completion Status
 - Discontinued Study
- Reasons for Discontinuation of Study

For the status of study completion and reasons for study drug and study discontinuation, the number and percentage of subjects in each category will be provided. The denominator for the percentage calculation will be the total number of subjects in the All Enrolled Analysis Set corresponding to that column.

The following by-subject listings will be provided by treatment arms and subject identification (ID) number in ascending order to support the above summary table:

- Reasons for study drug or study discontinuation.

4.2. Extent of Study Drug Exposure

Extent of exposure to study treatment will be summarized by treatment arms using descriptive statistics for total duration of exposure to study drug (idelalisib) including the number (ie, cumulative counts) and percentage of subjects exposed through the certain time periods. Summaries will be provided by treatment arms for the Safety Analysis Set.

Total duration of exposure to study drug (idelalisib) will be defined as last dosing date of study drug minus first dosing date plus 1, regardless of any temporary interruptions in study drug administration, and will be expressed in months using up to 1 decimal place (eg, 4.5 months). If the last study drug dosing date is missing, the latest date among the study drug end date, clinical visit date, laboratory sample collection date, and vital signs assessment date that occurred during the on-treatment period will be used for subjects included in the final analyses.

A by-subject listing of study drug administration will be provided by treatment arms and subject ID number (in ascending order), including dosing date, total duration of exposure to study drug and reason for dose interruption.

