3.3. Study Treatments

Subjects will be randomized to the following treatment arms:

- Arm A: Idelalisib 150 mg will be taken twice daily orally starting on Day 1 and administered continuously
- Arm C: Idelalisib 150 mg will be taken twice daily orally starting on Day 1 and administered continuously for 21 days, followed by 7 days of no study drug, within each 28-day cycle. Study drug should not be taken on scheduled “off-treatment” days, regardless of prior missed doses, study drug interruptions for toxicity, or PK samples.

The original protocol for this study included an Arm B, which was closed to enrollment as of Protocol Amendment 5.

- Arm B (closed to enrollment as of Protocol Amendment 5): 100 mg idelalisib will be taken twice daily orally starting on Day 1 and administered continuously. Subjects randomized to 100 mg twice daily with SD or PD may be dose escalated to 150 mg twice daily.

In case of administrative delays, every attempt should be made to initiate study drug as soon as possible, but no more than 7 days from randomization. If needed for toxicity management, a dose reduction is available as described in Section 5. The study drug, idelalisib, will be supplied by Gilead. The formulation, packaging, and dosing regimen are further described in Section 5.

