8.6.1. Extent of Exposure

Descriptive information will be provided by treatment arm regarding the duration of exposure to study drug, and the number and timing of dose interruptions and reductions.

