1.3. Study Design

This is a randomized, open-label, multi-center study that will be conducted globally.

Subjects will be randomized in a 1:1 ratio, until the enrollment target per arm is met, to the following treatment arms:

- Arm A: 150 mg twice daily idelalisib administered continuously
- Arm C: 150 mg twice daily idelalisib administered in 28-day cycles (21 days on-treatment, 7 days off-treatment)

[figure not shown]
The original protocol for this study included an Arm B, which was closed to enrollment as of Protocol Amendment 5.

- Arm B (*closed to enrollment as of Protocol Amendment 5*): 100 mg twice daily idelalisib administered continuously

[figure not shown]
Clinic visits will occur at Screening, Day 1, every 2 weeks through Week 12, every 4 weeks through Week 24, at Weeks 32, 36, 40, 48, and every 12 weeks thereafter through end of study (EOS). Subjects will be assessed for safety at each visit. Additional visits will be required between clinic visits for laboratory testing only.

Subjects will be assessed for FL disease status by continuous utilization of a single modality including positron emission tomography–computed tomography (PET-CT), CT, or MRI. If permanent discontinuation of idelalisib occurs prior to IRC documented progression of FL, subjects shall remain on study until progression of FL or withdrawal from the study for reasons specified in Section 3.5.2 of the Protocol Amendment 6.

Figure 1-1. Study Schema

Subjects enrolled prior to implementation of Protocol Amendment 5 followed the previous study design as shown here.

* Unblinding and dose modifications may occur at any time during study participation if the IRC Assessment confirms progressive disease.

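### The only by-arm exposure measure in the SAP counts Arm C's scheduled off weeks as exposure, and the protocol's summary of dose interruptions and reductions has been dropped

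*SAP*

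**What the plan says.** SAP section 4.2 defines total duration of exposure as the number of days from the first dosing date to the last, counting both, "regardless of any temporary interruptions in study drug administration". The by-arm summary is built on that one quantity, "using descriptive statistics for total duration of exposure to study drug (idelalisib) including the number (ie, cumulative counts) and percentage of subjects exposed" through successive time periods. Nothing is subtracted for planned off days. The SAP plans no summary of on-drug days, cumulative dose or dose intensity. Dosing dates and reasons for interruption appear only in a by-subject listing.

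The two arms open to enrolment since Amendment 5 are, in SAP section 1.3, "Arm A: 150 mg twice daily idelalisib administered continuously" and "Arm C: 150 mg twice daily idelalisib administered in 28-day cycles (21 days on-treatment, 7 days off-treatment". Protocol section 3.3 makes the off days strictly drug-free: "Study drug should not be taken on scheduled “off-treatment” days, regardless of prior missed doses, study drug interruptions for toxicity, or PK samples".

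Protocol section 8.6.1 promises, by arm, the duration of exposure and also "the number and timing of dose interruptions and reductions". SAP section 1 gives the SAP precedence where the two documents differ. SAP section 7.6, which records departures from the protocol's safety analyses, mentions only the time to onset of adverse events of interest.

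**The concern.** Arms A and C start at the same dose per administration and differ in schedule. Protocol section 1.4 states that the intermittent schedule lowers idelalisib exposure and rests the hoped-for reduction in toxicity on that. A reader comparing Grade 4 or higher event rates between the arms therefore needs to see how much drug each arm received. The only planned exposure table is nearly blind to the planned difference.

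The dropped protocol summary makes this harder to repair from the other tables. Without the number and timing of interruptions and reductions, a reader cannot tell whether Arm A's delivered dose drifted towards Arm C's through toxicity management, or whether Arm C had fewer unplanned interruptions, which protocol section 1.4 names as a possible benefit.

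**Working it through.** The documents state no exposure figure, so there is none to reproduce. The check applies the SAP 4.2 formula to each schedule.

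**Inputs**
- Arm A: drug on 28 of 28 days (SAP 1.3).
- Arm C: drug on 21 of 28 days, none on off days (SAP 1.3, protocol 3.3).
- Daily dose on a dosing day: 2 × 150 mg = 300 mg.
- Illustrative length: 48 weeks = 12 cycles, the follow-up named for the primary analysis in SAP 2.2.
- Assumptions: complete cycles, full dose, no unplanned interruption, equal time on treatment in both arms.

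**Formulas for c complete cycles**
- Arm A: span = on-drug days = 28c.
- Arm C: span = 28(c − 1) + 21 = 28c − 7. The final off week follows the last dose, so it is not counted.
- Arm C: on-drug days = 21c.
- Off days counted as exposure in Arm C = 7(c − 1).
- Overstatement factor in Arm C = (28c − 7)/(21c) = 4/3 − 1/(3c).

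**Results**

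| Cycles | Arm A span and on-drug days | Arm C span | Arm C on-drug days | Span ratio C/A | On-drug ratio C/A | Arm C span ÷ on-drug |
|---|---|---|---|---|---|---|
| 1 | 28 | 21 | 21 | 0.75 | 0.75 | 1.00 |
| 3 | 84 | 77 | 63 | 0.92 | 0.75 | 1.22 |
| 6 | 168 | 161 | 126 | 0.96 | 0.75 | 1.28 |
| 12 | 336 | 329 | 252 | 0.98 | 0.75 | 1.31 |
| 21 | 588 | 581 | 441 | 0.99 | 0.75 | 1.32 |

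At 12 cycles, 11 × 7 = 77 drug-free days are counted in Arm C, and 329/252 = 1.306, an overstatement of about 31%. The limit for long treatment is 28/21 = 1.333. In months, as SAP 4.2 reports duration (days/30.4375, my conversion), the table would show 11.0 against 10.8, with on-drug time 11.0 against 8.3. Cumulative dose would be 336 × 0.3 = 100.8 g against 252 × 0.3 = 75.6 g.

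From 6 cycles on, a planned 25% difference therefore appears as a difference of about 1% to 4%.

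**Interruptions and reductions, side by side**
- Protocol 8.6.1: number and timing of interruptions and reductions, by arm. SAP 4.2: no such summary.
- Protocol 8.6.2: a summary of adverse events leading to interruption, reduction or discontinuation. SAP 7.1.6.1: categories for temporary interruption and for discontinuation, none for reduction, although the secondary safety endpoint in SAP 1.2.2 includes events leading to reduction.
- SAP 7.6: neither omission is declared.

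**The case against.** Calendar span is a legitimate and openly defined measure, and the protocol never promised on-drug days, cumulative dose or dose intensity. The off week is part of Arm C's definition, so an informed reader knows that the planned fraction is 75%. The phrase about temporary interruptions does not name scheduled off weeks. The study was terminated early and its analysis is descriptive. All of this stands. But the last-minus-first formula includes the off weeks whatever that phrase was meant to cover, and knowing the planned 75% does not tell a reader what was delivered after interruptions and reductions.

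Four stronger readings might be inferred, and the documents do not support them:
- **The table would show identical exposure.** Off days after the last dose are not counted, so the spans are close but unequal, and in a single cycle the full 0.75 ratio shows. Different discontinuation patterns would also separate the arms.
- **Safety rates would have a wrong denominator.** Neither document plans an exposure-adjusted rate by arm; the adverse event summaries are counts and percentages of subjects. The problem would arise only if such a rate were added.
- **The primary results are affected.** Response rate and the incidence of Grade 4 or higher events are proportions of subjects and do not use exposure time.
- **Interruptions survive only in a listing.** SAP 7.1.6.1 tabulates by arm the adverse events leading to interruption. That covers subjects with event-driven interruptions, but not other causes, the number per subject or the timing.

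The plasma concentration summary in SAP section 8 does not fill the gap either: concentrations at scheduled visits do not measure cumulative dose, and protocol section 6.1.5.2 waives the predose sample when the prior dose fell in an off week.

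**Conclusion.** The point holds as a gap in reporting and interpretation. Calendar span is acceptable as a measure of time on treatment; the defect is that it is the only exposure measure by arm in a trial comparing a continuous with an intermittent schedule. Under full dosing, complete cycles and equal time on treatment, it overstates Arm C's on-drug time by about 31% at 12 cycles and shows a C/A ratio of 0.98 where the planned ratio is 0.75. Actual treatment durations are not in the documents, so the realised size is unknown. It shrinks with short treatment and cannot exceed one third under these assumptions; unplanned interruptions, which the rule also ignores, could add to it in either arm.

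Separately, and without depending on any of this arithmetic, the SAP omits the protocol 8.6.1 summary of interruptions and reductions and does not declare the omission.

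**What to change.** In SAP section 4.2:
- Keep the current measure and relabel it time on study treatment.
- Add by arm: on-drug days (excluding scheduled off days and interruptions), cumulative dose, and dose intensity relative to the arm's own planned schedule.
- Restore the protocol 8.6.1 summary of the number and timing of unplanned interruptions and reductions, kept separate from scheduled off days.
- Record in section 7.6 any part of that summary that is deliberately left out.

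SAP section 1 provides for changes after finalisation to be documented in the clinical study report, so these tables can still be added that way.

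The cost is SAP wording and a modest extra derivation from the dosing records. Dosing dates are already in the planned listing, and protocol section 9.1.5 requires the dose regimen in source data. Two things need checking first: that dose level is in the analysis database, since the SAP listing does not name it, and that the records allow scheduled off days to be told apart from unplanned interruptions.

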4.3. Protocol Deviations

Subjects who did not meet the eligibility criteria for study entry but enrolled in the study will be identified regardless of whether they were exempted by the sponsor or not. A by-subject listing will be provided for those subjects who did not meet at least 1 eligibility (inclusion or exclusion) criterion. The listing will present the eligibility criterion (or criteria if more than 1 deviation) that subjects did not meet and related comments, if collected.

Protocol deviations occurring after subjects entered the study are documented during routine monitoring. A by-subject listing will be provided for those subjects with important protocol deviations.

4.4. Assessment of COVID-19 Impact

This study was ongoing during the novel coronavirus (2019 nCoV [COVID-19]) pandemic, and the COVID-19 pandemic has caused a disruption in the regular visit schedules for this study. Some subjects were unable to attend onsite visits due to shelter-in-place guidelines, site closures, or other reasons. This section provides guidance on how to handle special situations due to COVID-19 in the analysis.

Adverse events (AEs) due to COVID-19 will be included in AE analyses if applicable. A by-subject listing of Adverse Events due to COVID-19 may be provided. The COVID-19 Standardized MedDRA Queries (SMQ) with Broad Scope in [Appendix 1](#) will be implemented.

4.4.1. Protocol Deviations Due to COVID-19

A by-subject listing will be provided for subjects with important protocol deviation related to COVID-19. A separate listing will be provided for subjects with non-important protocol deviation related to COVID-19.

4.4.2. Missed and Virtual Visits Due to COVID-19

A by-subject listing of subjects with missed or virtual visits due to COVID-19 will be provided by subject ID number in ascending order.

Information regarding virtual or missed visits due to COVID-19 was collected as free text in the CRF comment fields. The determination of missing or virtual visits due to COVID-19 was done using Natural Language Processing (NLP) to search the CRF comment fields. A detailed explanation of the algorithm is given in [Appendix 2](#).

5. BASELINE CHARACTERISTICS

5.1. Demographics

Subject demographic variables (ie, age, sex, race, and ethnicity) will be summarized for Safety Analysis Set using descriptive statistics for age, and using number and percentage of subjects for sex, race, and ethnicity.

A by-subject demographic listing, including the informed consent date, will be provided by subject ID number in ascending order for All Enrolled Analysis Set.

